PART B STUDY DESCRIPTION

TITLE OF PROTOCOL	Seizure-like Hippocampal Activity in Alzheimer's Disease Neurodegeneration		
Principal Investigator	[name].		
Co-Investigators	[name]; [name]; [name]		
Mailing Address	[name]		
E-Mail Address	[contact]		
P.I.'s Telephone	[name]	P.I.'s Pager [name]	Fax: [name]
Sponsor/Funding Source	Fidelity Biosciences Research Initiative; Neurology Department internal funding		

B1. PURPOSE OF PROTOCOL

To test the hypothesis that increased hippocampal perfusion on arterial spin labeling MRI in patients with Alzheimer's Disease (AD) is partially driven by focal epileptiform activity, and that this abnormal activity contributes to memory dysfunction.

Here we propose applying an imaging technique, arterial spin labeling MRI (ASL-MRI), ideally suited for testing this hypothesis. We will utilize a pharmacological probe, levetiracetam, to test whether sub-clinical epileptiform activity is driving increases in hippocampal perfusion and contributing to the declarative memory impairment in AD. Levetiracetam is an antiepileptic drug (AED) that inhibits epileptiform activity. Levetiracetam inhibits burst firing without affecting normal neuronal excitability. We will study patients with mild AD in three sessions, counterbalanced for order, in a crossover design. In each session, participants will undergo a baseline electroencephalogram (EEG). They will then be given either a placebo or intravenous levetiracetam low dose (2.5 mg/kg) or high dose (7.5 mg/kg). After drug administration, repeat EEG, ASL-MRI perfusion imaging, and behavioral testing will be conducted. Participants will return at 1-2 week intervals for the second and third sessions in the other conditions (levetiracetam low dose / levetiracetam high dose / placebo). This study will test whether increased hippocampal perfusion in AD is caused by epileptiform activity, whether this activity is contributing to memory impairment, and whether antiepileptic medications might be a new avenue of treatment in AD. If validated, ASL-MRI would be an ideal tool to non-invasively determine whether antiepileptic medications are effective in decreasing aberrant excitatory activity in the hippocampus in AD.

Aim 1: To determine whether increased hippocampal perfusion in AD is caused by epileptiform activity.

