Twenty subjects with mild AD (MMSE≥20) will participate in this study in the Clinical Research Center at Beth Israel Deaconess Medical Center. Subjects will be screened to ensure they meet inclusion and exclusion criteria and will provide written informed consent before any study procedures are performed. Each eligible subject will undergo three sessions, held 1-2 weeks apart, in a double blind, within-subject crossover design, counterbalanced for order (placebo / levetiracetam 2.5 mg/kg / levetiracetam 7.5 mg/kg), Figure 3. During each session, placebo or levetiracetam will be administered intravenously over 20 minutes. Drug administration will occur during EEG recording so that neurophysiological recordings can be acquired before, during, and after administration. Changes in EEG background frequency and level of synchrony will be analyzed⁴⁴⁻⁴⁶. After drug administration and EEG recording, hippocampal perfusion and functional connectivity will be measured with ASL-MRI and resting BOLD fMRI. Finally, participants will undergo a cognitive battery with memory tests particularly sensitive to hippocampal function (declarative memory, attention, working memory and executive function).

[figure not shown]

Figure 3. Overall paradigm. Participants will undergo testing in 3 sessions counterbalanced for order, with placebo, low dose LEV or higher dose LEV. Drug will be administered intravenously during EEG recording. Imaging will be acquired with anatomical, perfusion and resting state bold MRI. Cognitive testing will be performed with a battery including a memory test particularly sensitive to hippocampal function as well as other tests of frontal function.

2. Study Rationale

This protocol has three primary goals: to test the hypothesis that increased hippocampal perfusion in AD is at least partially driven by epileptic activity, that lowering epileptic activity may improve cognitive performance, and that perfusion MRI can be used as a non-invasive assay of the effects of medications that decrease epileptic activity in AD.

3. Subject Recruitment and Screening

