- h. 20 minutes before each dose of study drug, and at 10, 20, and 30 minutes after start of intravenous infusion of study drug: Systolic and diastolic blood pressure, heart rate, and respiratory rate
- i. Physical exam: appearance, cardiovascular, lung/chest, abdomen, extremities, and musculoskeletal.
- j. Neurological exam: mental status, cranial nerves, motor system, sensory system, reflexes, coordination, stance, gait
- k. Mini-Mental Status Examination
- l. Electroencephalogram

A 21-electrode array (Fp1, Fp2, F3, F4, C3, C4, P3, P4, O1, O2, F7, F8, T3, T4, T5, T6, Fz, Cz, Pz, reference, ground) of gold disc electrodes will be placed using paste technique, with electrode positions determined by the 10-20 International System.

Additional electrodes will be placed to monitor eye movements (superior and inferior to outer canthus of each eye) and electrocardiogram. EEG will be sampled at 250 Hz and band-pass filtered from 0.1-70Hz. EEG will be recorded for 20 minutes before, 20 minutes during, and 20 minutes after administration of study drug. During each 20 minute session, EEG will be recorded for 5 minutes with eyes open and 15 minutes resting with eyes closed. EEG will be analyzed using both visual and quantitative techniques ⁴⁴⁻⁴⁶. EEG will be visually inspected to determine 1) whether baseline epileptiform activity is present and is altered by study drug, and 2) whether study drug has other effects on EEG (such as diffuse slowing), which might affect the results of cognitive testing. Automated artifact detection and artifact decontamination filters will be used to minimize contributions of eye movements and other artifact sources. Data

segments containing possible artifacts will be excluded from analysis. For each session, EEG measures will include alpha peak power, beta band power, and delta/theta band power. will be determined for each session.

m. Study drug administration

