We plan to study 20-25 subjects at BIDMC. We anticipate screening 25 subjects to enroll and randomize 20 eligible subjects. We have performed a power calculation based on our previous study finding hyperperfusion of the hippocampus in AD as compared to controls ²³. With a sample size of 20 AD participants, we will have a 72% probability of detecting a decrease in perfusion after levetiracetam, assuming administration of the drug lowers hippocampal CBF only to normal levels. This estimate is likely overly conservative for two reasons. First, the within subject design should markedly decrease variance. Second, if epileptiform discharges are contributing to hippocampal hyperperfusion and damage, then briefly ceasing the abnormal activity with drug should reveal underlying hypoperfusion like that typically seen in temporal lobe epilepsy.

Data Analysis:

The primary study outcomes are:

- Differences in hippocampal perfusion on ASL-MRI
- Differences in memory performance

The secondary study outcomes are:

Differences in whole brain regional cerebral blood flow on ASL-MRI
Differences in working memory and executive functions
Differences in EEG measures (alpha peak power, beta band power, delta/theta band power, coherence)

Behavioral Data

Measures of memory encoding, retrieval and storage will be analyzed using repeated measures ANOVA. We will test our a priori main hypothesis of improved memory performance after drug. In a secondary analysis, we will measure effects of drug on working memory and executive functions in a similar manner.

Imaging Data

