We will do two analyses, one focused specifically on hippocampal perfusion and a second analyzing regional CBF throughout the whole brain. First, we will use a repeated measures ANOVA with hippocampal perfusion and session (placebo, 2.5mg/kg and 7.5mg/kg) being the factors. Hippocampal perfusion is measured as a percentage of visual cortex perfusion, using a template available within the Statistical Parametric Mapping package. Second, we will measure regional CBF throughout the whole brain using SPM5 and measure changes after drug vs. placebo using a random effects model and accounting for the repeated measures design. In addition to direct analysis of perfusion, we will examine cortical changes in CBF correlated with our seed region in the hippocampus. We predict that decreases in perfusion in the hippocampus after levetiracetam will correlate with increases in perfusion in association cortical regions. Lastly, we will test for correlations between behavioral measures of memory and regional changes in CBF in hippocampus and whole brain. We predict that decreases in hippocampal perfusion will paradoxically correlate with improved declarative memory performance.

EEG Data

EEG will be visually analyzed for presence of epileptiform activity. Peak alpha power, beta band power, delta/theta power, and coherence will be calculated using BESA (Brain Electrical Source Imaging) software and Persyst MagicMarker software. Measures will be analyzed using repeated measures ANOVA. We hypothesize that levetiracetam will decrease source coherence in temporal regions.

Analyses will be performed in the Cognitive Neurology Unit, Magnetic Resonance Imaging Center of the Department of Radiology, and EEG Laboratory at Beth Israel Deaconess Medical Center.

C. Subject Selection

Subjects will be recruited from the Cognitive Neurology Unit at BIDMC. The P.I., who specializes in neurodegenerative disorders, maintains an active clinic and treats over 100 patients with AD. In addition, the Cognitive Neurology Unit has over 13,000 patient visits per year.

Inclusion Criteria:

- Meets the NINCDS-ADRDA criteria for probable Alzheimer's disease
- Mild AD (MMSE \geq 20)
- Age \geq 50 years
- English as first language

Exclusion Criteria:

- A history of seizures prior to the onset of AD
- Familial Alzheimer's Disease due to known genetic mutations
- Current use of an anti-epileptic medication

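### The quantitative EEG analysis gives no role to the pre-infusion EEG recorded in every session; it should fix the analysis window and adjust for that session's baseline.

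*Combined protocol and SAP*

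**What the plan says.** Section B1 plans a baseline EEG in each session, before placebo or levetiracetam is given. Section B3.A.5, item l, sets the recording windows: "EEG will be recorded for 20 minutes before, 20 minutes during, and 20 minutes after administration of study drug". The Study Overview (B3.A.1) says that drug is given during the EEG so that "neurophysiological recordings can be acquired before, during, and after administration", and continues: "Changes in EEG background frequency and level of synchrony will be analyzed". It does not say whether the reference for a change is the pre-infusion epoch or the placebo session.

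Item l gives the baseline a use in the visual reading, which asks "whether baseline epileptiform activity is present and is altered by study drug". For the quantitative measures it says: "For each session, EEG measures will include alpha peak power, beta band power, and delta/theta band power". No window is attached to these values.

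Section B3.B lists EEG measures among the secondary outcomes. Its EEG Data paragraph adds a directional hypothesis (lower temporal source coherence on levetiracetam), and its model is one sentence: "Measures will be analyzed using repeated measures ANOVA". No factors or covariates are named. The only ANOVA factor spelled out in B3.B is session with three treatment levels, and that belongs to hippocampal perfusion.

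**The concern.** The crossover removes stable differences between patients. It does not remove variation from one visit to the next in the same patient, such as alertness, electrode placement and state on the day. The pre-infusion epoch measures that variation an hour or less before the outcome, and the plan does not say that the model will use it. With 20 patients, avoidable noise matters.

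The one-sentence model also leaves several analyses open: post-infusion values only, a value pooled over the whole recording, a change score, baseline adjustment, or a treatment-by-time interaction. They differ in precision, and one of them (pooling) shrinks the estimated effect. The choice should be made before the data are seen.

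**Working it through.** **Inputs from the documents.** 20 patients, three sessions each, and epochs of 20 minutes before, during and after infusion. The documents give no EEG effect size, standard deviation or pre/post correlation. The only power figure is 72%, for perfusion. It reproduces with 20 versus 20 treated as independent groups and two-sided α = 0.05 (assumed): difference 0.96 - 0.77 = 0.19; SD = √((0.29² + 0.17²)/2) = 0.2377; power = Φ(0.19/(0.2377 × √(2/20)) - 1.96) = 71.5%. It says nothing about EEG; 72% serves below only as a convenient starting point.

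**Assumption.** r is the correlation between pre- and post-infusion values within a session after patient effects are removed, with equal variance in both epochs. Since r is unknown, a range is shown.

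**Is the baseline a legitimate covariate?** It precedes that session's infusion. Sessions are at least 7 days (168 h) apart, and the quoted half-life in healthy elderly subjects is 10-11 h, so about 168/11 = 15 half-lives separate them. The earlier dose should not affect it materially.

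**Precision.** Contrast variance relative to post-infusion values alone:
- covariate adjustment: 1 - r²
- change score: 2(1 - r)
- difference between the two: 2(1 - r) - (1 - r²) = (1 - r)², never negative

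Apart from the small degree-of-freedom cost, a change score is therefore never more precise than adjustment, and it beats post-only values only when r exceeds 0.5. If the post-only contrast had 72% power (1.960 + 0.583 = 2.543 standard errors), power becomes Φ(2.543/√ratio - 1.960):

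| r | Adjusted: ratio | Adjusted: equivalent n, 20/(1 - r²) | Adjusted: power | Change score: ratio | Change score: power |
|---|---|---|---|---|---|
| 0 | 1.00 | 20 | 72% | 2.0 | 44% |
| 0.3 | 0.91 | 22 | 76% | 1.4 | 57.5% |
| 0.5 | 0.75 | 27 | 84% | 1.0 | 72% |
| 0.7 | 0.51 | 39 | 95% | 0.6 | 91% |

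The closed form ignores the cost of estimating the covariate slope. A simulation with 20 patients, three sessions, patient and treatment terms and an assumed effect of 0.7 residual SD (4,000 runs) includes it. Power was about 58% without baseline and 61%, 69% and 84% with it at r = 0.3, 0.5 and 0.7. At r = 0 about 1 to 2 points were lost. Type I error stayed near 5%. A separate paired simulation with a true effect of 0.82 recovered it (means 0.82) under post-only, change-score and adjusted analyses, so all three are unbiased.

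**Degrees of freedom.** 60 session values - 20 for patients - 2 for treatment = 38. The covariate leaves 37; adding visit leaves 35. The simulated power did not include visit, but the two-sided 5% critical t moves only from 2.026 (37) to 2.030 (35).

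**Dilution, only if all 60 minutes are pooled.** Let f be the share of the post-infusion effect already present during infusion, with equal correlation r between epochs. The pooled effect is (1 + f)/3 of the post-infusion effect, and the variance is (1 + 2r)/3 of a single epoch's. At r = 0.5 the variance factor is 2/3:
- f = 0: effect 33%, power 72% → 18%
- f = 0.5: effect 50%, power 72% → 34%
- f = 1: effect 67%, power 72% → 55%

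The effect always shrinks. Power usually falls but need not: at r = 0 and f = 1, averaging out noise raises it to 84%.

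**The case against.** The strongest reply is that the plan is silent here, not wrong. The visual reading explicitly compares with baseline. The overview's sentence on changes directly follows the one on recording before, during and after drug, so a pre-infusion reference is a natural reading. In item l, the word session also denotes a single 20-minute window, so measures for each session may mean one value per epoch. A repeated measures ANOVA could then include time, and its treatment-by-time term would use the baseline. All of this stands. A reader might infer that the baseline EEG is ignored altogether; the documents do not support that.

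It does not close the gap. No sentence gives the quantitative model a time factor, a baseline or a window. In a treatment-by-time ANOVA, the treatment main effect averages over pre-drug data; only the interaction isolates the drug effect, and the plan does not say which is tested. The post-minus-pre part of that interaction is a change score, which adjustment matches or beats.

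It is also fair that the gain is assumed rather than shown: each patient is already their own control, the gain at r = 0.3 is small, and at r = 0 there is a slight loss. Finally, the protocol itself regards surface EEG as very limited for detecting hippocampal epileptic activity, and no primary conclusion rests on these measures. That limits the severity.

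**Conclusion.** The point holds for the quantitative EEG measures only: the plan assigns no role to a baseline that it collects at every session, and baseline adjustment is a better-defined and generally more precise analysis. The size depends on r, which the documents do not give. Over an assumed range of 0.3 to 0.7, contrast variance falls by 9% to 49%; at r = 0 there is no gain and a loss of about 1 to 2 power points.

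Two stronger conclusions are not supported. One is that the planned analysis certainly loses precision: that requires both a post-only comparison, which is not stated, and a worthwhile r. The other is that the drug effect will be diluted: a post-only comparison dilutes nothing, and pooling pre-infusion minutes is merely not excluded by the wording.

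Severity is minor, because EEG is a secondary outcome with no power claim attached.

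**What to change.** In the EEG Data paragraph of B3.B, state that:
- the outcome is each quantitative measure in the 20-minute post-infusion epoch, with pre-infusion data kept out of the outcome value;
- the same measure from that session's pre-infusion epoch is a covariate in the repeated measures model, with patient, treatment and visit;
- patient effects are fixed, or the covariate is split into the patient's mean baseline and the session's deviation from it, so that the adjustment acts on within-patient variation;
- the during-infusion epoch is descriptive, or has some other named use.

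Covariate adjustment is preferable to a plain change score, which adds variance when r is below 0.5.

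The cost is a few lines of text, one degree of freedom for the covariate and two for visit. No extra data are needed.

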- Current use of a medication known to lower seizure threshold (e.g. bupropion or a neuroleptic)
- Presence of parkinsonism
- Significant cerebrovascular disease
- Other Central Nervous System disease (e.g. stroke, severe traumatic brain injury)
- Major depression or other psychiatric or behavioral disorders (psychosis, agitation)
- Medical contraindication to MRI (e.g. cardiac pacemaker, intraocular or intracranial metallic objects)
- Severe claustrophobia or inability to lie flat for MRI
- Known allergy to levetiracetam, or history of previous adverse reaction to levetiracetam
- Serum creatinine \geq 2

Participants receiving standard treatments for dementia including cholinesterase inhibitors, memantine and serotonergic selective reuptake inhibitors may participate.

B4. POSSIBLE BENEFITS

The present study is designed to enhance our understanding of the role of epileptiform activity in Alzheimer's disease. There is no direct benefit to the subject from participating in this study.

Confirmation of a relationship between excitatory neuronal activity and cognitive deficits in humans with AD would provide new insights into the pathogenesis of AD. If levetiracetam decreases this excitatory activity, antiepileptic drugs may be a new potential avenue for treatment or prevention of AD.

B5. POSSIBLE RISKS AND ANALYSIS OF RISK/BENEFIT RATIO

Several aspects of this trial have a potential for subject discomfort or injury. All study procedures are low- to moderate-risk procedures, as described below. These risks are balanced by the potential benefit that the knowledge gained from this research may help to determine new methods to treat or prevent Alzheimer's Disease.

Study drug: Levetiracetam has been approved by the FDA as safe and effective in the treatment of seizures and epilepsy and is generally well tolerated. No laboratory monitoring is recommended by the FDA for patients receiving levetiracetam for seizures. Levetiracetam may cause some, all, or none of the side-effects listed below. Subjects will receive only one dose of study medication at each visit, so side effects should not last longer than 12-24 hours.

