More Common: The most frequently reported side effects from levetiracetam are drowsiness, dizziness, nausea, and headache. Other side effects can include vomiting, tremor, irritability, or depression. More than 10% of subjects may experience these side effects when levetiracetam is given intravenously. The side effects are usually mild and temporary. The medication will be given slowly over 20 minutes to minimize these side effects.

Less Common: Less common side effects (occurring in 1-10% of subjects) include anger, anxiety, decreased appetite, diarrhea, and infection (colds or viral infections).

Rare: Rare side effects (occurring in less than 1% of subjects) include severe depression or the development of suicidal thoughts, effects on blood cells (low blood counts, low platelets or white blood cells), liver failure and weight loss.

Blood draws: The risks and discomforts of blood drawing from a vein include the possibility of pain or bruising at the site of the blood draw; occasional feeling of lightheadedness; and rarely, infection at the site of the blood draw.

Intravenous catheter placement and medication infusion: Levetiracetam and placebo will be given through an intravenous catheter. Possible risks of the catheter or infusion include: skin infection at the catheter site; redness, swelling, discomfort, pain, or bruising at the injection (IV) site; bruising of the skin caused by broken blood vessels leaking blood under the skin; or local thrombosis.

EEG: EEG is a commonly used procedure which has low risk. Some subjects experience mild discomfort during scalp preparation for electrode placement, or have itching or skin irritation at the electrode site. Some subjects find it difficult to lie still during the EEG, which will last approximately one hour.

MRI scans are safe and routinely used in medical diagnosis. Exposure to strong, static magnetic fields is accepted as safe. Subjects will be screened for MRI safety, including presence of metal in their body. For this protocol, all MRI studies will be performed on a 3T General Electric research magnet that has received FDA approval. There is no exposure to ionizing radiation. This technique is non-invasive and does not require administration of exogenous contrast agents. The most common adverse event associated with MRI is claustrophobia. Subjects will have voice contact with the technologist performing the study at

all times, and the MRI scan can be immediately stopped at the subject's request.

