- Who will use or disclose that information
- The rights of a research subject to revoke their authorization for use of their PHI.

In the event that a subject revokes authorization to collect or use PHI, the investigator, by regulation, retains the ability to use all information collected prior to the revocation of subject authorization.

Subject binders will be kept in a locked cabinet accessible only to the investigators. For data analysis, data will be entered into a password-protected computerized database behind the BIDMC firewall. The investigator will retain study essential documents for at least 2 years after completion of the study.

General Safety

All safety considerations were included as part of the design of this study.

Data Safety Monitoring Plan

Monitoring of Adverse Events: While levetiracetam is not used in treating Alzheimer's disease, it is widely used in the treatment of epilepsy, including epilepsy that develops in patients with Alzheimer's disease. We will be using a single dose, so the risk of side effects is low.

Participants will complete the side effects questionnaire prior to and after every session in order to evaluate side effects.

The occurrence of any unexpected undesirable side effect will result in holding the trial until communication with the IRB, the CRC administrative staff, and the Research Subject Advocate

has taken place, and the risk for participants reassessed. Participation in the study for any given participant will stop in the event of any unexpected side effects or any cognitive deterioration as measured by the serial assessments described above.

Reporting of Adverse Events: All adverse events will be reported and reviewed every week according to laboratory policies. Information about all adverse events relating to this study will be collected and reported on the attached Report of Adverse Event Form. Any adverse event occurring in participants after they sign the consent form and until two weeks after the trial will be reported according to the following guidelines:

- (1) All fatal, life-threatening or serious adverse events will be reported verbally ([name]) and faxed ([name]) to the CRC RSSO Director and the CCI within 24 hours.
- (2) Unexpected serious adverse events will be reported verbally in real time to the CCI and the CRC RSSO Director.
- (3) Unexpected moderate adverse events will be reported in writing to the CCI and the CRC RSSO Director within 10 days of occurrence or recognition.

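### B8's participant-stop rule never turns on seriousness, so a serious side effect regarded as expected, without measured cognitive deterioration, does not oblige anyone to withhold the remaining infusions

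*Combined protocol and SAP*

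**What the plan says.** The Data Safety Monitoring Plan in B8 contains two rules that lead to action.

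- Participant stop: "Participation in the study for any given participant will stop in the event of any unexpected side effects or any cognitive deterioration". The deterioration is the kind measured by the study's serial assessments.
- Trial hold: "The occurrence of any unexpected undesirable side effect will result in holding the trial until communication with the IRB". Two further parties, the Research Subject Advocate and CRC administrators, must also be contacted.

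The remaining provisions concern reporting and review.

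- "All fatal, life-threatening or serious adverse events will be reported verbally" and by fax, within 24 hours, to the CRC RSSO Director and the CCI.
- "Unexpected serious adverse events will be reported verbally in real time to the CCI and the CRC RSSO Director".
- "All adverse events will be reported and reviewed every week according to laboratory policies".
- An annual summary goes to the CRC RSSO.

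Under B3.A (Study Overview, and Crossover Design, Randomization, and Blinding), each participant attends three sessions 1-2 weeks apart and receives placebo, 2.5 mg/kg and 7.5 mg/kg levetiracetam in one of six orders. Patients and investigators are blinded.

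**The concern.** Both side-effect triggers depend on whether the effect was unexpected. Neither depends on how bad it was. Read literally, a trivial effect nobody foresaw must end participation, while a serious effect that was foreseen need not. Nothing in the documents explains that ordering.

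This matters because the study re-doses by design. The single dose that B8 refers to is one dose per visit, so over three visits every participant is due two active infusions. After a serious effect of the first, whether the second is withheld depends on how an undefined word is read, or on discretion. Blinding adds to the difficulty: the investigator cannot know whether the event followed drug or placebo, or whether the next infusion is active. What is at stake is participant safety. No estimate or test in the analysis is affected.

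**Working it through.** **1. The rules side by side.** No figure in the plan needs reproducing here. The check is which event triggers which rule.

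| Event | Trial hold | Participant stop | Reporting |
|---|---|---|---|
| Unexpected undesirable side effect, any severity | Yes | Yes | Weekly review; faster if moderate or serious |
| Side effect regarded as expected, with measured cognitive deterioration | No | Yes | Weekly review; 24 hours if serious |
| Serious side effect regarded as expected, no measured cognitive deterioration | No | No | 24-hour report, weekly review, annual summary |

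The third row is the gap.

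**2. Does the plan recognise that row?** Yes. The first reporting item covers all serious events. The second sets a faster route for those that are also unexpected. The split makes sense only if some serious events are not unexpected.

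**3. Does anything else require withholding?** I found nothing in the documents.

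- The Study Plan (B3.A.6) lists examinations at visits 1-3 but no re-dosing criterion. The neurological examination precedes the infusion; the cognitive battery follows it.
- Telephone follow-up collects adverse effects only.
- The exclusion for a previous reaction to levetiracetam (B3.C) is an entry criterion.
- The right to discontinue (B6) is the participant's choice.

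**4. Could a serious effect be called expected?** The documents point both ways. B5 names such effects in advance: "Rare side effects (occurring in less than 1% of subjects) include severe depression or the development of suicidal thoughts, effects on blood cells", and the same sentence goes on to liver failure. Against that, B8 says "We will be using a single dose, so the risk of side effects is low" and B5 says "Subjects will receive only one dose of study medication at each visit, so side effects should not last longer than 12-24 hours". Two investigators could classify the same event differently, and the text does not settle it.

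**5. What remains after the first active infusion?** Inputs: the six sequences in B3.A.4, reading A as placebo, B as 2.5 mg/kg and C as 7.5 mg/kg in the order listed.

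| Sequence | Active infusions left | Next session active? | Sessions left |
|---|---|---|---|
| ABC | 1 | Yes | 1 |
| ACB | 1 | Yes | 1 |
| BAC | 1 | No (placebo) | 2 |
| BCA | 1 | Yes | 2 |
| CAB | 1 | No (placebo) | 2 |
| CBA | 1 | Yes | 2 |

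One active infusion remains in 6 of 6 and is the very next session in 4 of 6. In 3 of 6 (ABC, BAC, BCA) it is the higher dose. Mean sessions left, weighting the sequences equally: (1 + 1 + 2 + 2 + 2 + 2)/6 = 10/6 = 1.67.

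**6. How often could a listed rare effect occur?** Inputs: under 1% of subjects (B5), taken per listed effect; 20 participants (B3.B). All results are upper bounds.

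- Any occurrence: 20 × 0.01 = 0.2 participants; chance of at least one, 1 − 0.99^20 = 18.2%.
- At the first active infusion, assuming the 1% covers both active infusions and splits equally: 20 × 0.005 = 0.1; 1 − 0.995^20 = 9.5%.
- At the first active infusion, assuming 1% applies to each infusion: 0.2 and 18.2% again.

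B5 does not say its rates are for single doses, so the true figures may be lower.

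**The case against.** The strongest reply is that the existing triggers already catch nearly everything that matters. The protocol expects single-dose effects to be mild, brief and low in risk, so liver failure or suicidal thoughts after one infusion would surprise most investigators, and both rules would then apply. The cognitive trigger has no severity threshold. Mental status is examined at every visit and a cognitive battery is given each session, so a serious neurological or psychiatric effect in mild AD could well meet it. A 24-hour report and a weekly review would generally come before the next session. Side-effect questionnaires, telephone follow-up and family involvement add further checks. This largely stands. It shows the gap is narrow, but none of these measures makes withholding mandatory for an event in the third row of the table.

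A reader might infer that B8 has no mandatory stop for serious side effects at all. The documents do not support that: serious effects judged unexpected, or accompanied by measured cognitive deterioration, do stop the participant. Nor do they support inferring that participants would in practice be re-dosed after a serious event. The protocol does not require withholding, but clinical judgement would probably lead to it. The weekly review also follows laboratory policies that are not part of the documents, so the finding is confined to the protocol text.

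It can also be said that *serious* is undefined too, and that judging whether another cause is clear is a further judgement. That is fair, but B8 already requires staff to classify events as serious within 24 hours for reporting, so the fix relies on a decision they must make anyway.

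**Conclusion.** The concern holds in a limited form. The participant-stop rule turns on unexpectedness or cognitive deterioration, never on seriousness. A serious effect that is regarded as expected and comes without measured cognitive deterioration leads to reports and review but to no required withholding, although one active infusion always remains after the first.

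The conclusion rests on an investigator reading *unexpected* so as to leave the event out, which the text permits but does not compel. The 9.5% and 18.2% figures bound the occurrence of one listed effect under the stated assumptions. A reader might take them as the chance of harmful re-dosing. They are not: the event would also have to be serious, be judged expected, come without measured cognitive deterioration, and be followed by another active infusion despite the 24-hour report. The documents give no rate for any of those steps.

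Severity is minor to should-fix, with moderate confidence. The case rests on the gravity of the possible event and the low cost of the remedy, not on frequency.

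**What to change.** Add to the stop sentence in B8: *or any life-threatening or serious adverse event that cannot be clearly attributed to a cause other than study drug, whether or not expected*. State that this cancels that participant's remaining infusions. Keep the existing triggers. The wording can be applied without unblinding.

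Do not make the B5 side-effect list the reference for *unexpected*. That would make suicidal thoughts or low blood counts formally expected and so narrow the present protection.

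Extending the trial-wide hold to the same events is optional. It is not needed to close the gap, and a hold could push other participants outside the 1-2 week interval.

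The cost is one reworded sentence and a small IRB amendment, with no added visit, test or staff. An affected participant loses at most two sessions: after an event at the first active infusion, one in ABC and ACB and two in the other four sequences. Some of these losses may be for events that later prove unrelated. One limit remains: the only planned blood tests are urea nitrogen and creatinine at screening, so blood-count or liver effects would trigger the rule only if clinically apparent.
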